INVESTIGATOR'S ABBREVIATED PROTOCOL

1. TITLE: Prasugrel for prevention of early saphenous vein graft thrombosis

2. PRINCIPAL INVESTIGATOR: [name], PhD

CO-INVESTIGATOR: [name]

KEY MEMBERS: [name]

[name]

[name]

[name]

[name]

[name]

[name]

[name]

3. SPONSOR OF THE STUDY: VA Merit, VA OR&D

4. IND/ IDE: Not Applicable

5. PURPOSE OF THE STUDY, INCLUDING HYPOTHESIS TO BE TESTED:

Aortocoronary saphenous vein graft failure is common and is associated with high morbidity and mortality. Thrombus formation plays a critical role in early saphenous vein graft occlusion and may predispose to subsequent atherosclerosis formation. Optical coherence tomography is a novel, high-resolution, intravascular imaging technique that can reliably identify thrombus. Based on the findings of earlier VA Cooperative Studies, aspirin significantly reduces the incidence of early saphenous vein graft failure and is currently used in nearly all patients undergoing coronary bypass graft surgery. Administration of clopidogrel for improving early saphenous vein graft patency has provided conflicting results in small randomized studies. Prasugrel is a novel thienopyridine that provides more rapid, consistent, and intense platelet inhibition than clopidogrel. However, in patients who undergo coronary artery bypass graft surgery, it remains unknown whether prasugrel may decrease thrombus formation in saphenous vein grafts during the first postoperative year, and whether this will result in less saphenous vein graft wall thickening, less lipid deposition in the saphenous vein graft wall and fewer clinical events without increasing the risk for severe bleeding.

We hypothesize that in patients undergoing clinically-indicated coronary artery bypass graft surgery, administration of prasugrel starting at dismissal from the index coronary bypass graft surgery hospitalization will result in lower prevalence of thrombus formation in a target SVG, as assessed by optical coherence tomography performed 12 months post surgery compared to placebo, with similar incidence of major bleeding.

6. BACKGROUND AND RESULTS OF PREVIOUS RELATED RESEARCH:

Saphenous vein graft failure

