One SVG will be examined in each patient. The target intermediate SVG lesion will be selected by the interventional cardiologist performing the procedure as the longest and least-angulated SVG amenable to intravascular imaging. After intragraft administration of 200 µg of nitroglycerin, an OCT catheter (DragonFly, St Jude Medical, Minneapolis, Minnesota) will be advanced 40-50 mm distal to the SVG proximal anastomosis and will be pulled back proximal to the lesion using a motorized system at a speed of 20 mm/sec. The OCT images will be written on CD-R or DVD for subsequent off-line analysis. Subsequently, a 45-MHz, 3.2F, rotational IVUS catheter (Revolution, Volcano therapeutics, Rancho Cordova, California, USA) will be advanced into the target SVG and the transducer will be advanced as distal as possible within the SVG and will then be pulled back to the SVG aortic ostium using a motorized pull-back system at a speed of 0.5 mm/s. During pullback, gray-scale IVUS will be recorded at a rate of 30 frames per second. The gray-scale IVUS movie will be written on CD-R or DVD for subsequent off-line analysis. Similarly, a 3.2-F near-infrared spectroscopy catheter (Lipiscan IVUS, InfraReDx, Burlington, Massachusetts) will be advanced into the target SVG and positioned to the same location where the IVUS catheter was previously placed, if feasible. The catheter will then be pulled back to the aortic ostium using a motorized pull-back system at a speed of 0.5 cm/s. A chemogram of the artery will be obtained, as shown in Figures 10-12. The near-infrared spectroscopy data will also be recorded in CD-R or DVD for subsequent analysis.

Examination of the target SVG lesion with angiography, OCT, IVUS, and NIRS will be obtained at 12 months post CABG. If the patient undergoes clinically-indicated graft angiography before the 12-month planned angiography, then: (a) if ≥ 10 months have elapsed from enrollment in the study, then angiography, OCT, IVUS, and NIRS of a target SVG will be performed; or (b) if <10 months have elapsed from enrollment, then prasugrel will be continued and the patient will be asked to return for the planned 12-month angiography, OCT, IVUS and NIRS.

Follow-Up: Study procedures and follow-up assessments are summarized in the below table 2.

Table 2. Schedule of observations and laboratory assessments.

Test	Treatment period						Post-Treatment Follow-up Contact (30 days after 12 month visit – Phone FU)

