	0	1m +/- 5 days	3m +/- 10 days (phone FU)	6m +/- 10 days	9m +/- 10 days (phone FU)	12m +/- 30 days	
Inclusion/Exclusion criteria reviewed	X						
Informed consent	X						
Medical history	X	X	X	X	X	X	X
Physical examination/ Vital Signs	X	X		X		X	
Medication adherence		X	X	X	X	X	
Electrocardiogram	X					X	
SVG angiography, OCT, IVUS and NIRS						X	

FU=follow-up; SVG=saphenous vein graft; IVUS=intravascular ultrasonography; NIRS = near-infrared spectroscopy; OCT = optical coherence tomography

13. ANTICIPATED DATA AND DATA ANALYSIS:

Expected treatment effect

A recent study demonstrated the presence of thrombus in 25% of SVGs examined early post CABG.⁴⁷ Given the potent antiplatelet effect of prasugrel, we anticipate 80% reduction in the prevalence of thrombus in SVGs, as assessed by OCT.

Sample size calculation

Assuming that thrombus will be detected by OCT in 25% of patients in the placebo group vs. 5% of patients in the prasugrel group (80% relative reduction), the sample size required to detect the specified difference with 80% power and a 2-sided α

level of .05 is 48 patients per group, which was increased to 60 patients to allow for 20% dropout.

Assuming 48 patients are evaluable in each group, the power of the study assuming a prevalence of thrombus by OCT in the control arm of 20%, 25%, and 30% will be 67%, 80%, and 89%, respectively.

Enrolling 40 patients per year for three consecutive years will require enrollment of 25 % of the eligible patients at our institution. Enrollment rate in the SOS trial which also required angiographic and IVUS follow-up⁶² was 56%, suggesting that enrollment of the projected number of patients is feasible in our setting.

Statistical Analysis of primary endpoints

All endpoints (primary and secondary) will be analyzed with an intent-to-treat approach.

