The prevalence of thrombus within the target SVG at 12-month OCT imaging (primary efficacy endpoint) will be analyzed using the Fisher's exact test. In view of the relatively small sample size of the trial, multivariable logistic regression analyses will be performed to adjust the findings for any potential differences in the baseline characteristics of the two study groups, which are known to influence the occurrence of SVG failure. Such characteristics are: patient age, prior myocardial infarction; total cholesterol and HDL-cholesterol levels; minimum graft diameter; mean arterial pressure; ejection fraction; male gender; and current smoking.⁶⁹ The significant characteristics will be incorporated in the calculation of an adjusted odds ratio representing the association between treatment and the prevalence of thrombus, along with 95% confidence intervals. Because off-pump and endoscopic SVG harvesting may be associated with higher rates of SVG failure, randomization will be stratified by (a) on vs. off pump and (b) endoscopic vs. open harvesting.

The time elapsed to the incidence of severe bleeding, defined using the GUSTO criteria⁶⁷ (primary safety endpoint) will evaluated using Kaplan-Meier survival curves and compared between the 2 study groups using the log-rank test.

Statistical Analysis of secondary endpoints:

The differences in angiographic SVG failure, in total and normalized total SVG atheroma volume and in lipid core burden index at 12-month SVG imaging will be compared between the 2 study groups using Fisher's exact test. A logistic regression model will be developed to evaluate the treatment effect on this outcome adjusting for patient age, prior myocardial infarction; total cholesterol and HDL-cholesterol levels; minimum graft diameter; mean arterial pressure; ejection fraction; male gender; and current smoking.⁶⁹

The incidence of major adverse cardiovascular events (composite of death, acute coronary syndrome, and coronary revascularization) at 12 months will be compared between the two study groups using the chi-square test. Kaplan-Meier survival curves and the log-rank test will be used to compare time-to-event of major adverse cardiac events in the two study groups.

All tests will be two-sided. The critical level for the primary and four secondary outcomes will be 0.05. No adjustments will be made for multiple secondary endpoints

14. PROVISIONS FOR MANAGING ADVERSE REACTIONS:

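### The target vein graft is picked at the 12-month procedure from grafts that can be imaged, with no rule for an occluded graft, so the primary OCT comparison is conditioned on post-randomisation patency

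*Combined protocol and SAP*

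**What the plan says.** - **Selection.** Section 12 (Catheterization, OCT, IVUS, and NIRS) has one graft examined per patient. The target "will be selected by the interventional cardiologist performing the procedure as the longest and least-angulated SVG amenable to intravascular imaging". The OCT catheter must pass 40-50 mm beyond the proximal anastomosis.
- **Timing.** Imaging is at 12 months after surgery, or at a clinically indicated angiogram from 10 months after enrolment. For an earlier angiogram, "if <10 months have elapsed from enrollment, then prasugrel will be continued and the patient will be asked to return" for the planned imaging; nothing is said about recording a target found occluded then. Table 2 shows no graft imaging before 12 months. Study drug starts at hospital discharge (section 11).
- **Primary endpoint.** Section 13 defines it as "The prevalence of thrombus within the target SVG at 12-month OCT imaging (primary efficacy endpoint"), compared by Fisher's exact test.
- **Analysis set.** "All endpoints (primary and secondary) will be analyzed with an intent-to-treat approach". No rule is given for an occluded graft or one that cannot be imaged.
- **Sample size.** "Assuming that thrombus will be detected by OCT in 25% of patients in the placebo group vs. 5% of patients in the prasugrel group", giving 48 per group, raised to 60 for 20% dropout.
- **Rationale.** The title is "Prasugrel for prevention of early saphenous vein graft thrombosis", and section 5 states: "Thrombus formation plays a critical role in early saphenous vein graft occlusion". Figure 3's legend presents early occlusion and intimal thickening as the two alternative courses of a graft.
- **Where occlusion is counted.** Only in the secondary endpoint of angiographic failure (at least 75% stenosis in at least one vein graft, section 11).

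**The concern.** Patency at 12 months is a post-randomisation state. If prasugrel changes the chance that a graft occludes, it also changes which grafts are available for selection, and the imaged grafts are then no longer a randomised comparison. Blinded reading does not prevent this, because the selection works through the drug's effect on patency and not through anyone's knowledge of the arm.

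A patient whose best graft has thrombosed completely either leaves the primary analysis or is scored on another, open graft, possibly as free of thrombus. The plan does not say which. The most severe form of the outcome in the title can thus be missing from the primary endpoint, or count as a success. The result would still answer the literal hypothesis in section 5 (OCT thrombus in a target graft at 12 months), but it could not by itself support a claim that prasugrel prevents graft thrombosis.

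**Working it through.** **1. The plan's own figure.** Pooled normal formula, two-sided alpha 0.05, 80% power, 25% versus 5%:

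n = [1.960·√(2·0.15·0.85) + 0.842·√(0.25·0.75 + 0.05·0.95)]² / 0.20² = 48.8, so 49 against 48 stated. 48/0.80 = 60. Power at 48 per group with an 80% reduction from control rates of 20%, 25% and 30% is 68.0%, 79.3% and 87.7%, against 67%, 80% and 89% stated. The figures reproduce. The concern is selection, not this calculation.

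**2. How many patients could be affected** (rates from sections 6 and 7, applied to 48 per group):

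- At least one occluded vein graft at 30 days, placebo 23.1%, clopidogrel 17.5%: 11.1 and 8.4 patients.
- Failure of at least one vein graft in year 1, 29%-46%: 13.9 to 22.1 patients. Not all failures are occlusions.
- Per-graft non-patency, aspirin versus aspirin plus clopidogrel: 5%/5% and 6.5%/3.7% in the two 12-month trials, 14.3%/8.4% in the 3-month trial. That is 2.4, 3.1 and 6.9 of 48 placebo targets, against 0.25 × 48 = 12 expected placebo events.

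**3. What an observed 25% versus 5% could mean.** Assumptions: per-graft rates apply to the target, occluded targets are not imaged, and no graft occludes because of treatment. Let o₁ and o₂ be placebo and prasugrel occlusion. The share of imaged prasugrel grafts that would have occluded on placebo is r = (o₁ − o₂)/(1 − o₂). The prasugrel prevalence q in grafts open under either arm satisfies (1 − r)q + r·t = 0.05, where t, the thrombus rate in the extra open grafts, lies anywhere from 0 to 1. So q lies between max(0, (0.05 − r)/(1 − r)) and 0.05/(1 − r). The composite of occlusion or thrombus is c = o + (1 − o)p, where p is the 25% or 5% seen in imaged grafts.

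| o₁/o₂ | r | q | Difference from 25% (points) | Composite, placebo vs prasugrel | Composite difference (points) |
|---|---|---|---|---|---|
| 5%/5% | 0 | 5.0% | 20.0 | 28.8% vs 9.8% | 19.0 |
| 6.5%/3.7% | 0.0291 | 2.2% to 5.1% | 19.9 to 22.8 | 29.9% vs 8.5% | 21.4 |
| 14.3%/8.4% | 0.0644 | 0 to 5.3% | 19.7 to 25.0 | 35.7% vs 13.0% | 22.7 |

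**4. The same mechanism run forward.** Hold the true effect in always-open grafts at 80%, use 14.3%/8.4%, and let every graft kept open by treatment carry thrombus. Placebo thrombus per patient is 0.25 × 0.857 = 0.2143. On prasugrel it is 0.2 × 0.2143 + 0.059 = 0.1019. Among imaged prasugrel grafts the rate is 0.1019/0.916 = 11.1%. The trial would see 25% versus 11.1%, a 56% reduction instead of 80%.

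**5. Effect of losing occluded targets on the OCT test.** Exact Fisher power for 25% versus 5% is 72% at 48/48. With imaged n = 48(1 − o), it is 72% at 46/46, 78% at 45/46 and 74% at 41/44. Exact power is not monotone in n, so this reads as no material loss.

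**The case against.** **The document is abbreviated.** It refers to an attached Sponsor's Protocol that may hold the missing rule. This stands as a limit: the point concerns these documents. But the selection rule they state, followed exactly, already excludes or swaps out occluded grafts.

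**Occlusion is not lost from the trial.** A closed graft meets the angiographic failure definition, and the 20% allowance may absorb patients who cannot be imaged. True, but the first is a separate any-graft secondary endpoint and the second protects numbers, not comparability. Neither says how an occluded target enters the primary analysis.

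**Any OCT endpoint needs an open lumen, and the endpoint matches the hypothesis.** Accepted. What follows is a limit on the conclusion, plus the avoidable problem of substitution after the outcome has occurred.

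**The illustrated bias is small.** In the table the always-open difference is at most 0.3 points below the observed 20.0, and most of the range means the plan understates benefit. Neither cited 12-month clopidogrel trial shows a significant patency difference. This stands for that set of assumptions. Step 4, with another set, gives a much larger distortion, so the assumptions decide the size. Substitution by another open graft is not quantified at all.

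**The remedy is imperfect.** No section says the operative report records angulation, some pre-named grafts will be hard to image, and some occlusions will be non-thrombotic or predate study drug. Occluded targets still leave the OCT comparison. All of this stands. It is why the occlusion analysis is proposed as supporting and not as a replacement for the primary endpoint.

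**Conclusion.** The concern holds; it should be fixed, with medium confidence. Choosing the target at the imaging procedure from imageable grafts conditions the primary comparison on post-randomisation patency, and these documents give no rule for an occluded target. That an occluded graft is not imageable is an inference, but a strong one given the catheter placement required.

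The size and direction of the bias are unknown. The figures above borrow clopidogrel trial rates, treat per-graft rates as target-graft rates, and assume treatment causes no occlusion. If occlusion is equal in the two arms, the modelled bias is nil. As written, the trial could not show afterwards whether its imaged grafts were comparable.

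**What to change.** 1. **Section 12 (Catheterization, OCT, IVUS, and NIRS).** Name the target graft at randomisation, before allocation is known, by a fixed rule on features recorded in the operative report, for example a pre-ranked list of the patient's vein grafts. Allow a reserve graft only for listed anatomical reasons, never because the target is occluded. Report by arm how many targets were occluded, replaced or not imaged. If the Sponsor's Protocol already has a target-graft or occlusion-scoring rule, bring sections 12 and 13 into line with it.
2. **Section 13 (Statistical Analysis of primary endpoints).** Pre-specify a supporting analysis in all randomised patients with 12-month graft outcome data. Count as an event a target occluded at the 12-month angiogram, or documented occluded earlier and not imaged later, as well as OCT thrombus. Report it beside the OCT comparison, and limit conclusions from OCT alone to patent, imageable grafts.

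**Cost.** Wording and one item from the operative report. Operative data are needed at that point anyway, since "randomization will be stratified by (a) on vs. off pump and (b) endoscopic vs. open harvesting" and section 8 excludes multiple distal anastomoses. Patency comes from the angiogram already in Table 2. The primary endpoint and sample size do not change.

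Making the composite primary is optional and not part of this fix. At 48 per group including occluded targets, its exact Fisher power would be 57%, 70% and 68% under 5%/5%, 6.5%/3.7% and 14.3%/8.4% occlusion, and 80% would need 75, 59 and 62 per group. If it were chosen, power should be restated under declared occlusion rates.

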Approximately 120 patients will be randomized into this study at the Dallas VA Medical Center.

10. JUSTIFICATION FOR THE USE OF SPECIAL SUBJECT POPULATIONS:

Not applicable.

11. STUDY DESIGN:

The primary efficacy objective is to compare the prevalence of SVG thrombus as detected by optical coherence tomography of a target SVG between patients receiving prasugrel vs. placebo. We hypothesize that prasugrel will be superior to placebo in reducing the prevalence of SVG thrombus at 12-month follow-up OCT imaging.

The primary safety endpoint is the incidence of severe bleeding as defined using the GUSTO study criteria.⁶⁷ We hypothesize that patients receiving prasugrel will have similar incidence of severe bleeding compared to patients receiving placebo during the 12-month study period.

The secondary endpoints will be: (1) incidence of angiographic SVG failure (defined as $\geq 75\%$ SVG diameter stenosis in at least one SVG); the total and normalized total SVG atheroma volume within at least 40 mm of the target SVG, as assessed by intravascular ultrasonography; the lipid core burden index of the target SVG, as assessed by near-infrared intracoronary spectroscopy; and (2) the incidence of major adverse cardiac events and moderate bleeding during the 12-month study period.

The proposed study is a phase 3, single-center, randomized, double-blind, controlled, parallel-group study of prasugrel vs. matching placebo in patients with recent CABG, starting at the time of hospital dismissal from CABG (Figure 13). All patients will be receiving aspirin, as per standard current practice.

[figure not shown]

Figure 13: Flowchart of the proposed study design.

CABG = coronary artery bypass graft surgery; OCT = optical coherence tomography; IVUS = intravascular ultrasound; NIRS = near-infrared spectroscopy; R = randomization; m = month; FU = follow-up.

12. DESCRIPTION OF PROCEDURES TO BE PERFORMED:

The study design will be explained to the patients and if they agree to participate they will be asked to sign an informed consent form and they will receive a copy of the consent form. They will subsequently be randomized to prasugrel or placebo, as described below.

Randomization and Treatment

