For safety monitoring, any emergency adverse event resulting from participation in the study will be treated at the Dallas VA Medical Center. [name] will evaluate all adverse events and determine the appropriate course of action.

If a patient develops severe bleeding during the study period, prasugrel will be temporarily held and will be discontinued if the patient is considered to be at increased risk for recurrent bleeding. If a patient develops an indication for receiving oral anticoagulation therapy with warfarin or dabigatran during his or her participation in the study, prasugrel administration will be discontinued to minimize the risk of bleeding.

If any subjects are hospitalized for an acute coronary syndrome or undergo coronary angiography at an outside hospital, the hospitalization records will be obtained and reviewed by the clinical events committee. The Universal definition of myocardial infarction will be used for diagnosing myocardial infarction. Bleeding will be assessed with the use of the GUSTO criteria.⁶⁷ Severe bleeding will be defined as fatal bleeding, intracranial hemorrhage, or bleeding causing hemodynamic compromise requiring blood or fluid replacement, inotropes, or surgery.⁶⁷ The frequencies of moderate bleeding, defined as bleeding requiring transfusion not characterized as severe, and moderate/severe and severe bleeding will also be analyzed. Information on (surgical or percutaneous) coronary revascularization will also be collected. Data will be entered on paper-based case report forms and will be double-entered into a secure, password protected database, accessible only by study personnel. Subjects will be identified by a unique study number in the database.

Additionally a Data Safety Monitoring Board will be appointed to review the study periodically (every 12 months, or sooner if required).

15. RISK/ BENEFIT ASSESSMENT:

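### Angiographic SVG failure is compared only at 12-month imaging, so a graft that fails, is treated before month 10 and is open at month 12 can be counted as not failed

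*Combined protocol and SAP*

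**What the plan says.** - **Endpoint (section 11, secondary endpoints).** The "incidence of angiographic SVG failure", meaning a diameter stenosis of 75% or more in at least one SVG. The definition itself gives no time window.
- **Analysis (section 13, secondary endpoints).** What is compared between arms is "The differences in angiographic SVG failure, in total and normalized total SVG atheroma volume and in lipid core burden index at 12-month SVG imaging", by Fisher's exact test with a logistic model for adjustment.
- **Clinically indicated graft angiography before the planned study (section 12, catheterization).** There are two branches. If at least "10 months have elapsed from enrollment in the study, then angiography, OCT, IVUS, and NIRS of a target SVG will be performed". Otherwise, "if <10 months have elapsed from enrollment, then prasugrel will be continued and the patient will be asked to return" for the planned 12-month imaging.
- **Schedule (Table 2).** SVG angiography appears only at the 12-month visit.
- **Other capture of the event.** Section 14 states: "Information on (surgical or percutaneous) coronary revascularization will also be collected". It also has outside-hospital angiography records reviewed by the clinical events committee. Section 13 defines MACE as the "composite of death, acute coronary syndrome, and coronary revascularization".
- **Analysis principle (section 13).** "All endpoints (primary and secondary) will be analyzed with an intent-to-treat approach".

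**The concern.** An incidence over the first postoperative year and a status at month 12 are different quantities when a failed graft can be reopened in between. The protocol makes that a realistic path: section 7 calls percutaneous intervention the currently preferred treatment for severe SVG lesions, and section 6 describes thrombus forming in grafts immediately after surgery. The 12-month comparison can therefore miss failures that were found and successfully treated early. SVG failure is the trial's direct measure of what prasugrel is meant to prevent, and for these patients the plan gives no rule other than their month-12 appearance.

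**Working it through.** **1. The plan's own sizing, for reference.** The only sample size is for the primary OCT-thrombus endpoint: 25% vs 5%, two-sided 0.05, 80% power.

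n = [1.96·√(2·0.15·0.85) + 0.8416·√(0.25·0.75 + 0.05·0.95)]² / 0.20² = (0.990 + 0.408)² / 0.04 ≈ 48.8, so 49 per group against the stated 48. Then 48 / 0.80 = 60, as stated.

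The same normal approximation at 48 per group, with an 80% relative reduction, gives power of 68%, 79% and 88% at control rates of 20%, 25% and 30% (stated 67%, 80%, 89%). The sizing reproduces closely and this point does not affect it. No power is claimed for SVG failure.

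**2. One patient followed through the text.** A graft reaches 75% stenosis or more at month 5, is found on clinically indicated angiography and is stented.
- Section 12: fewer than 10 months have elapsed, so the patient returns at month 12.
- Section 13: the comparison uses month-12 imaging. If the graft is then below 75% and no other SVG has failed, the patient is scored as not failed.
- Section 14 records the revascularization and section 13 counts it in MACE. No sentence sends it to the SVG failure endpoint.
- The intent-to-treat statement settles which arm the patient belongs to, not how an interim failure is classified.

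**3. Effect on the comparison.** Let p_C and p_T be the true cumulative failure risks on placebo and prasugrel, and e_C and e_T the shares of failures treated before month 10 and read as open at month 12.

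Observed risks: p_C(1 − e_C) and p_T(1 − e_T).
Observed relative risk: (p_T/p_C)·(1 − e_T)/(1 − e_C).

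If e_C = e_T = e, the relative risk is unchanged and the absolute difference is multiplied by (1 − e). If the shares differ, the relative risk moves. With a true relative risk of 0.50:
- e_C = 30%, e_T = 10%: 0.50 × 0.90/0.70 = 0.64 (diluted).
- e_C = 10%, e_T = 30%: 0.50 × 0.70/0.90 = 0.39 (exaggerated).

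**4. Illustrative power.** Assumptions: true failure 40% vs 20% (40% lies within the 29%–46% first-year range in section 7; the halving is assumed), 48 evaluable per arm, two-sided Fisher's exact test at 0.05, exact enumeration.

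| Share erased | Both arms: observed rates | Power | Placebo only: observed rates | Power |
|---|---|---|---|---|
| 0% | 40% vs 20% | 49% | 40% vs 20% | 49% |
| 10% | 36% vs 18% | 43% | 36% vs 20% | 33% |
| 20% | 32% vs 16% | 37% | 32% vs 20% | 20% |
| 30% | 28% vs 14% | 30% | 28% vs 20% | 10% |

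The placebo-only columns are the extreme case.

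Across the protocol's range, again with an assumed relative risk of 0.5 and equal erasure of 10%–30%, normal-approximation power falls from 40% to 36%–28% at a control risk of 29%, and from 66% to 59%–45% at 46%.

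**The case against.** Several points on the other side are fair.

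- **The event is not lost to the trial.** Revascularization counts in MACE, which is tested by chi-square and log-rank. This stands, but MACE mixes death, acute coronary syndrome and any coronary revascularization, so it does not say whether a graft failed.
- **Misclassification needs several conditions.** Silent, untreated or re-narrowed grafts still count at month 12, and so does a patient with another failed SVG. Section 7 itself reports frequent in-stent restenosis and mentions native-artery intervention, which could leave the graft failed. This stands and limits how often the problem arises.
- **Incidence may already mean cumulative.** Possibly, but then sections 11 and 13 disagree and must be reconciled.
- **This is an abbreviated protocol that refers to an attached sponsor's protocol.** A rule could be there. In the text available there is none.

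A reader might also go further than the documents allow, in four ways:

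- **That the endpoint is biased towards no difference.** More failures on placebo does not mean a larger share of them is erased, and step 3 shows that bias can run either way.
- **That the rule discards the failures the trial aims to prevent.** It affects one secondary endpoint and, within it, only grafts successfully treated before month 10.
- **That stented segments will enter the OCT, IVUS and NIRS measures.** They may. The target is the longest, least-angulated SVG suitable for imaging, which need not be the treated one, and OCT starts only 40–50 mm beyond the proximal anastomosis.
- **That the same lesion found after month 10 is certain to count as failed.** Section 12 says study imaging is performed then, but not whether before or after any treatment.

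**Conclusion.** The concern holds as a gap in the definition of a secondary endpoint. As written, the plan can score a patient with a documented and treated graft failure as not failed, which does not match an incidence over the study period. Failure is undercounted. Equal proportional loss leaves the relative risk unchanged and shrinks the absolute difference by the share erased; unequal loss can dilute or exaggerate the relative effect. On the illustrative assumptions above, equal loss of 10%–30% takes power from 49% to between 43% and 30%, and the placebo-only extreme takes it as low as 10%. The true rates, the treatment effect on SVG failure and the share treated before month 10 are not in the documents, so these figures show sensitivity and are not a forecast. The primary endpoint's sizing is unaffected. The point should be fixed, but it does not threaten the trial's main analysis.

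**What to change.** 1. **Define the endpoint cumulatively in sections 11 and 13.** Failure is a stenosis of 75% or more, or occlusion, of any SVG on any angiogram from randomization through the 12-month study angiogram. A graft revascularized for such a lesion counts as failed whatever its later appearance. Tying this to a qualifying lesion keeps the protocol's own threshold; counting every SVG revascularization would abandon it.
2. **Read interim graft angiograms blinded to arm, by the same process** as the study angiograms.
3. **Report 12-month-only status as a sensitivity analysis.**
4. **Report target-SVG OCT, IVUS and NIRS results with and without grafts treated before imaging.** A treated graft should not be relabelled as having thrombus, because stenosis and thrombus are different findings.

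The cost is a few sentences of protocol and analysis text, plus the reading of angiograms that already exist; section 14 already collects revascularization data and outside-hospital records. The downside is small: early failures would rest on clinical rather than protocol angiograms, and clinically driven detection may differ by arm. The 12-month-only sensitivity analysis helps to show whether that matters.
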